### **3.8.3. Selection of Data in the Event of Multiple Records in a Window**

Depending on the statistical analysis method, single values may be required for each analysis window. For example, change from baseline by visit usually requires a single value per visit. Unless otherwise noted throughout the rest of this document, when a single value is needed, the following rule(s) will be used:

- If more than 1 assessment occurs during the same nominal visit, select the record closest to the nominal day for that visit.
- If there are 2 assessments that are equidistant from the nominal day, the data of the assessment after the scheduled study day will be used.
- The last measurement will be used if multiple measurements are taken on the same day.

## 4. SUBJECT DISPOSITION

### 4.1. Subject Enrollment

The number and percentage of subjects treated with IDELA will be summarized. A listing of subjects treated will be provided to describe site, subject number, informed consent date, screening date, and date of first dose of IDELA.

A listing of screen failed subjects will be provided to include date of informed consent and the reasons for screen failing.

### 4.2. Disposition of Subjects

A summary of subject disposition will be provided. This summary will present number of subjects:

- screened
- treated with study drug (ie, ITT analysis set)
- treatment ongoing
- treatment completed due to disease progression or death
- discontinued the study treatment (with summary of reasons for not completing),
- entered the 5-year long-term follow-up
- in the PP, pharmacodynamic and pharmacokinetic analysis sets

The denominator for the percentages of subjects in each category will be the number of subjects in the ITT analysis set.

Subjects who completed and discontinued long-term follow-up through 5 years will be summarized separately. The reasons for not completing the 5-year follow-up will be summarized as well.

A data listing of reasons for premature study treatment discontinuation will be provided along with subject number, site number, first and last dosing date, duration of treatment, and last contact date. The most recent, non-missing primary and key secondary endpoint values prior to discontinuation will also be included in this listing.

#### **4.3. Extent of Exposure**

##### **4.3.1. Duration of Exposure to Study Drug**

Duration of exposure to study drug will be defined as (min(last dose date, data cutoff date) – first dose date + 1), regardless of temporary interruptions in study drug administration, and will be expressed in months. Duration of exposure to study drug will be summarized for ITT analysis set using descriptive statistics and as the number and percentage of subjects exposed for at least 1 day, 2, 4, 6, 12 months, and every 6 months thereafter.

Number and percentage of subjects who had dose modification (dose reduction and dose re-escalation) will also be summarized.

IDELA dosing records, drug accountability (dispense and return) records and dose modification records will be listed in details.

##### **4.3.2. Adherence (Compliance) with Study Drug**

Adherence (%) with study drug will be calculated as:

Adherence (%) = {sum of pills dispensed minus pills returned for each dosing period} divided by {sum over all dosing period of (total daily pills x dosing duration)}, taking into account physician-prescribed reductions, escalations and interruptions.

Descriptive statistics for adherence along with the number and percentage of subjects belonging to adherence categories (eg,  $< 80\%$  or  $\geq 80\%$ ) will be provided for the ITT analysis set. No inferential statistics will be provided.

#### **4.4. Protocol Deviations**

Protocol deviations will be identified by the Gilead clinical team. Major protocol deviations will be summarized by type of deviation in the clinical study report (CSR) based on ITT analysis set. A listing will be provided for all major protocol deviations.

## 5. BASELINE DATA

### 5.1. Demographics and Baseline Characteristics

Demography including gender, race, ethnicity, age (years), weight (kg), height (cm) and body mass index (BMI, kg/m^2) will be summarized for the ITT analysis set.

Age will be calculated as the number of years between date of birth and date of first dose.

Age (years) = (date of first dose – date of birth+1) / 365.25 (round down to an integer)

BMI (kg/m^2) = weight / (height) (round to 1 decimal point)

Number and percentage of subjects <65 and ≥65 years will also be summarized. A data listing will be presented for date of birth and the above demographic data. ECOG performance status collected at the baseline will also be summarized.

### 5.2. Medical History

Summary tables will be provided based on the ITT analysis set.

#### 5.2.1. Indolent NHL Disease History/Status

Number and percent of subjects with different types of disease history (as categorized in the CRF) for indolent Non-Hodgkin lymphoma (iNHL) and results for organ assessment will be summarized using ITT analysis set. Data listings will be presented separately for iNHL history and organ assessments. Time since disease diagnosis (in years) will also be summarized using descriptive statistics.

All disease history with partial diagnosis date will be identified and the partial dates will be imputed as follows:

- If day and month are missing but year is available, then the imputed day and month will be 01 Jan.
- If day is missing but the month and year are available, then the imputed day will be the first day of the month.

No imputation will be done if the year of diagnosis is missing.

A similar summary will be provided for the PP analysis set.

### **5.2.2. General Medical History**

Medical conditions will be coded to system organ class (SOC), high level term (HLT), and preferred term (PT) using Medical Dictionary for Regulatory Activities (MedDRA) coding dictionary version 15.1. Ongoing medical conditions will be graded per Common Terminology Criteria for Adverse Events (CTCAE) Version 3.0 (1=Mild, 2=Moderate, 3=Severe, 4=Life-threatening or disabling and 5=Fatal).

General medical history, history of liver disease and clinically significant elevated transaminase (alanine aminotransferase/aspartate aminotransferase) or bilirubin will be summarized by SOC, HLT, and PT. The summary will be sorted in descending frequency by SOC, HLT, and PT. Data will be listed for the 3 types of histories separately.

Ongoing general medical history will be summarized separately by SOC, HLT, PT, and severity.

## 6. EFFICACY ANALYSES

Imaging-based tumor assessments will be performed within 28 days prior to the start of treatment. On-study tumor assessments will be performed at ~8- to 12-week intervals at visits 1, 6, 9, 11, 13, and 15 (corresponding to baseline, Weeks 8, 16, 24, 36, and 48) and every 12 weeks thereafter. An end-of-treatment tumor assessment (if the subject withdraws from the study for reasons other than tumor progression on a routine imaging/scan) should be performed if the last assessment was performed > 4 weeks prior to end-of-treatment visit.

Imaging-based tumor assessments include site of lesion and bi-dimensional measures for the largest diameter and the perpendicular diameter. Tumor response will be evaluated by both investigators and IRC.

Data will be presented for both investigators assessments and IRC assessments. A subject's response status at each visit, best overall response (BOR), date of progression and date of first response will be determined by IRC and recorded in the IRC database. The findings of IRC will be considered primary for analyses of ORR and other tumor control endpoints (ie, DOR, TTR, % changes in tumor size and PFS). Consistency of evaluation between IRC and investigator assessments will be summarized by the percent agreement for overall response.

### 6.1. Definition of the Primary Efficacy Endpoint

A best overall response of CR, PR, stable disease (SD), PD, not evaluable (NE) and no disease (ND) is allowed. For subjects with WM, a minor response (MR) is also allowed. In the event that a single PD is followed by an assessment that is SD, PR or CR which is the same or better than the prior nadir response and there is substantial interruption of exposure to study drug, that PD may not be considered in the BOR evaluation in accordance with the Gilead Protocol 101-09 Imaging Charter.

ORR is defined as the proportion of subjects who achieve a CR or PR (or MR for subjects with WM) during the IDELA treatment. The response definitions for each category are based on standard criteria and defined in Section 8.1.5 of the protocol. Subjects who do not have sufficient baseline or on-study tumor status information to be adequately assessed for response status (ie, those with best overall responses of NE or ND) will be included in the denominators in calculations of response rates.

### 6.2. Statistical Hypothesis for the Primary Efficacy Endpoint

The study will test the hypothesis that ORR is  $\geq 39\%$  (i.e.  $\geq \sim 40\%$ ) against the null hypothesis that it is  $\leq 20\%$ .

### **6.3. Analysis of the Primary Efficacy Endpoint**

The ORR and 95% CI will be presented along with the corresponding p-value from the exact binomial test. The number and proportion of subjects who were evaluated as CR, PR, SD, PD, NE, and ND will also be tabulated.

The primary analysis for ORR will be conducted in the ITT set based on the IRC assessments. The investigator assessments will also be summarized. Both investigator and IRC assessments for tumor response will be listed in detail including site of lesion, date and method of evaluation, bidirectional measures and sum of the products of the perpendicular diameters of measurable index lesions (SPD). Summaries will also be provided for response at each visit separately when tumor assessment is available.

Agreement in best overall response between IRC and investigator assessments will be summarized.

### **6.4. Secondary Efficacy Endpoints**

#### **6.4.1. Definition of Secondary Efficacy Endpoints**

- DOR – defined as the interval from the first documentation of CR or PR (or MR for WM subjects) to the earlier of the first documentation of disease progression or death from any cause
- LNR – defined as the proportion of subjects who achieve a  $\geq 50\%$  decrease from baseline in the SPD
- TTR – defined as the interval from the start of study drug to the first documentation of CR or PR (or MR for WM subjects)
- PFS – defined as the interval from the start of study drug to the earlier of the first documentation of disease progression or death from any cause
- OS - defined as the interval from the date of first IDELA to death from any cause
- Changes in HRQL as reported by subjects using the FACT-Lym
- Changes in performance status as documented using the Karnofsky performance criteria

#### **6.4.2. Analysis Methods for Secondary Efficacy Endpoints**

##### **6.4.2.1. Duration of Response and Progression-Free Survival**

The date of definitive progression will be the timepoint at which progression is first identified by relevant radiographic or imaging data. Death occurring  $\leq$  30 days following the discontinuation of study drug will be considered as an event for the DOR and PFS calculation. Data will be censored on the date of the last tumor assessment (including assessments with a NE outcome) for subjects

- who do not have disease progression or die within 30 days after discontinuation of the study drug, or
- who start new anti-tumor therapy prior to documented disease progression, or
- who have 2 or more consecutive missing tumor assessments before disease progression or death.

Subjects without adequate baseline tumor response evaluation will be censored on Study Day 1. PFS will also be summarized for responding subjects (ie, subjects with a CR or PR) and non-responding subjects separately.

To assess the robustness of the primary DOR and PFS results, the following sensitivity analyses will be performed:

- DOR and PFS will be assessed based on IRC assessments using the PP analysis set based on the same censoring rules as above.
- DOR and PFS will be assessed based on investigators assessments using the same censoring rules as above.
- DOR and PFS will be assessed based on the first PD identified by IRC without consideration of any drug interruption or the response status post that PD with all other censoring rules staying the same as the primary analysis.

PPD

DOR and PFS will be summarized using KM methods and KM curves for DOR and PFS will be provided. All the derived endpoints will be listed.

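### The PFS and DOR censoring date has no limit in time, so a subject who misses two or more scans and then progresses is literally censored at the progression scan, not before the gap

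*SAP*

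**What the plan says.** SAP Section 6.4.1 defines PFS as "the interval from the start of study drug to the earlier of the first documentation of disease progression or death from any cause". DOR ends at the same events but starts at first response.

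Section 6.4.2.1 dates progression from imaging: "The date of definitive progression will be the timepoint at which progression is first identified by relevant radiographic or imaging data". It counts a death up to 30 days after stopping study drug as an event. It then gives one censoring date: "Data will be censored on the date of the last tumor assessment (including assessments with a NE outcome) for subjects" in any of three groups:

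- those with neither progression nor death within 30 days of stopping study drug;
- those "who start new anti-tumor therapy prior to documented disease progression, or"
- those "who have 2 or more consecutive missing tumor assessments before disease progression or death".

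A separate sentence reads: "Subjects without adequate baseline tumor response evaluation will be censored on Study Day 1".

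No visible section restricts the date in the second and third groups to scans before the new therapy or before the missed scans. The three visible sensitivity analyses keep the same censoring rules. A further block in that section is redacted.

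**The concern.** The second and third groups are defined by something that happens before progression, so both include subjects who later have documented progression on imaging. For them the progression scan is a tumor assessment, and it is on file. Read as written, the last tumor assessment is then the progression scan, or a later one.

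Two things follow for a subject with missed scans. The progression is not counted, which the rule intends. The subject also stays in the risk set through the unobserved gap and up to the progression date, which a missed-scan rule exists to prevent. Such subjects enlarge the denominator at every event time in the gap and push the Kaplan-Meier curve up. Two programmers, one reading the words and one assuming the usual convention, would produce different PFS and DOR data sets.

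A smaller matter sits beside this. The Day 1 rule makes no mention of death, while the same section counts deaths in the event window as events. The order of precedence is not stated.

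**Working it through.** **The plan's own figure.** The SAP gives no event count, precision or power for PFS or DOR, so there is no stated figure to reproduce.

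**Inputs from the SAP.** Scans at Weeks 8, 16, 24, 36 and 48, then every 12 weeks (Section 6); the censoring rule (Section 6.4.2.1); 125 subjects enrolled (Section 1.3).

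**Step 1: missed scans.** Stable disease at Week 24, Weeks 36 and 48 missed, progression at Week 60.

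| Reading | Censoring date | At risk at Weeks 36, 48 and 60 |
|---|---|---|
| As written | Week 60 | yes |
| Last scan before the gap | Week 24 | no |

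The difference is 60 − 24 = 36 weeks. A further scan at Week 72 would put the literal date 72 − 60 = 12 weeks past progression. For DOR in a responder the start date is the same under both readings, so the difference is again 36 weeks. If the gap ends in death with no scan in between, the last assessment is already the one before the gap and nothing is over-credited.

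**Step 2: new therapy.** Suppose the last scan is at Week 24 and new therapy starts at Week 28. With no further scan, both readings give Week 24. With a progression scan at Week 36, the literal date is Week 36 and the limited date Week 24, a difference of 12 weeks. So this group is affected only if a scan follows the new therapy. In the Schedule of Assessments (Section 1.2), as the table can be read, the radiology marks end at the end-of-treatment visit.

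**Step 3: the Day 1 rule beside the death rule.** Section 6.4.2.1 says without qualification that a death within 30 days of stopping drug is an event. Section 3.1.2 removes from the per-protocol set subjects who have no PFS event and also lack the tumor evaluations, which implies that a subject without those evaluations can have a PFS event. The Day 1 sentence, applied first, would censor that subject. The passages can be reconciled, but the SAP does not say which comes first.

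**Step 4: size.** All rates below are assumptions.

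*Simulation A.* N = 125, 400 replicates, exponential progression, 96 weeks of scans, scans continuing after new therapy. New therapy and a two-scan gap are each assigned to the stated share of subjects regardless of progression. The medians are means over replicates, and each single estimate falls on a scan week.

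| True median (weeks) | Share in each group | Week-48 PFS, as written | Week-48 PFS, limited date | Difference (points) | KM median (weeks), as written vs limited |
|---|---|---|---|---|---|
| 32 | 5% | 36.6% | 34.9% | 1.7 | 38.58 vs 37.71 |
| 32 | 10% | 38.5% | 35.0% | 3.5 | 40.14 vs 38.07 |
| 32 | 20% | 42.1% | 35.2% | 6.9 | 42.69 vs 38.10 |
| 48 | 5% | 51.4% | 49.9% | 1.5 | 56.79 vs 54.48 |
| 48 | 10% | 53.1% | 50.0% | 3.1 | 59.34 vs 54.54 |
| 48 | 20% | 56.1% | 50.2% | 5.9 | 68.25 vs 54.81 |

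The true Week-48 values are 0.5^(48/32) = 35.4% and 0.5^(48/48) = 50.0%. When gaps and new therapy are unrelated to progression, the limited date recovers the truth and the literal date does not. The differences are on the high side for the SAP, because scans continue after new therapy and because subjects who never progress within 96 weeks are also treated as affected.

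*Simulation B.* N = 125, true median 48 weeks, follow-up 24 to 89 weeks. Only subjects who progress are put in the two groups, and a gap is possible only after at least two earlier scans. Week-48 PFS without any such censoring is 50%.

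| Share of progressors in each group | As written | Limited date | Difference (points) | Difference if no scan follows new therapy |
|---|---|---|---|---|
| 5% | 52.9% | 52.2% | 0.7 | about 0.4 |
| 10% | 56.6% | 55.3% | 1.3 | about 0.9 |

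Here most of the upward shift remains after the fix: 52.2 − 50 = 2.2 of 2.9 points at 5%, and 55.3 − 50 = 5.3 of 6.6 points at 10%. That part comes from censoring the progressions at all, not from the date.

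**The case against.** The strongest defence is that the usual convention is understood and that a statistician would censor before the gap without being told. That does not stand as a reason to leave the text alone. Where this SAP wants a limit it writes one: the best SPD change is confined to time on treatment (Section 6.4.2.2), and transaminase censoring takes the earliest of listed dates (Section 7.2.5).

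Other parts of the defence do stand, and they bar several stronger readings that a reader might infer:

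- *That new therapy routinely adds progression-free time.* This needs scans after the new therapy starts. The visible schedule plans none after end of treatment, and Section 7.8 only lists post-study therapy. Therapy begun while still on study drug, or unscheduled scans, could produce the effect.
- *That counting NE scans is an error.* It is an explicit choice. Section 6.1 treats NE as too little information to judge response, so such a scan does not show absence of progression. For example, stable disease at Week 16 and NE at Week 24 as the last scan gives 24 − 16 = 8 weeks without support. The overall effect was not sized, and excluding these scans is a preference.
- *That the Day 1 rule removes deaths.* The same section counts such deaths as events and Section 3.1.2 points the same way. What is missing is the order of precedence. Measurable disease is an entry criterion (Section 1.2), so few subjects should be concerned.
- *That no sensitivity analysis tests the date.* This can be said only of the three visible ones.
- *That correcting the date removes the upward bias.* The corrected rule still censors the same progressions. Simulation B shows most of the shift remaining when the gap or new therapy is tied to progression.

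**Conclusion.** The point holds for subjects with two or more consecutive missed assessments followed by progression on imaging: the written rule gives a wrong censoring date. In the worked case it is 36 weeks too late. For new therapy it holds only where a scan is done after the therapy starts. The Day 1 rule needs a stated precedence and no more.

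The effect is upward, because for the subjects concerned the literal date is never earlier than the limited one. Its size is not known. The simulations give about 0.4 to 0.9 points at Week 48 if 5% or 10% of progressors fall in each group and no scan follows new therapy, and 1.5 to 6.9 points under the less restrictive assumptions of Simulation A. The matching shift in the median in Simulation A is about 1 to 13 weeks. The SAP gives none of these rates.

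PFS and DOR are secondary Kaplan-Meier summaries in a single arm with no hypothesis test, and the primary ORR test is untouched. This is a wording correction worth making before the data sets are programmed; it does not put the trial's main conclusion in doubt.

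**What to change.** In Section 6.4.2.1, keep the present date for the first group and give the other two their own:

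- *Missed assessments:* censor at the last tumor assessment before the first of the consecutive missed assessments.
- *New anti-tumor therapy:* censor at the last tumor assessment on or before the start of that therapy.

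Add to the Day 1 sentence that a death on study drug or within 30 days of stopping it takes precedence and counts as an event. This reconciles the sentence with the death rule in the same section and with Section 3.1.2.

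Optional: use the last evaluable (non-NE) assessment, and add a sensitivity analysis that counts later progression or death as an event despite a gap or new therapy. Only such an analysis would address the dropped events.

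The cost is a few lines of SAP text and one date derivation. PFS and DOR estimates become slightly shorter, by an amount that depends on how often scans are missed and new therapy is started.

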### **3. GENERAL CONSIDERATIONS FOR DATA ANALYSES**

#### **3.1. Analysis Sets**

##### **3.1.1. Intent-to-Treat Analysis Set**

The intent-to-treat (ITT) analysis set will comprise all subjects who receive  $\geq 1$  dose of IDELA. The ITT analysis set will be used in the analyses of ORR, progression-free survival (PFS), overall survival (OS), safety, and study drug administration and compliance. The ITT analysis set will be the primary analysis set for all the efficacy variables.

Duration of response (DOR) and time-to-response (TTR) will be analyzed based on all ITT subjects who achieve a CR or PR (including MR for subjects with WM). Lymph node response rate (LNR) will be analyzed based on all ITT subjects who have both baseline and  $\geq 1$  evaluable post-baseline tumor assessments.

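### PFS and DOR are censored at the last scan even when it was read as not evaluable, which can raise both Kaplan-Meier curves but, if such reads carry no progression information, cannot lower them

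*SAP*

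**What the plan says.** SAP Section 6.4.2.1 fixes the censoring date for both endpoints: "Data will be censored on the date of the last tumor assessment (including assessments with a NE outcome) for subjects" in any of three groups:

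- those "who do not have disease progression or die within 30 days after discontinuation of the study drug, or"
- those "who start new anti-tumor therapy prior to documented disease progression, or"
- those "who have 2 or more consecutive missing tumor assessments before disease progression or death"

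Subjects with an inadequate baseline evaluation are censored on Study Day 1. There is no matching provision for a subject whose post-baseline scans are all NE. The estimator is Kaplan-Meier: "DOR and PFS will be summarized using KM methods and KM curves for DOR and PFS will be provided".

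Section 6.1 uses NE, as a best overall response, for subjects without enough tumor information "to be adequately assessed for response status (ie, those with best overall responses of NE or ND". It keeps them in the ORR denominator, where they count as non-responders.

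Three sensitivity analyses for DOR and PFS are visible in Section 6.4.2.1: the per-protocol set, investigator assessments, and the first IRC progression. The first two repeat the primary censoring rules. The third changes only how progression is identified. A redacted block follows them.

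**The concern.** A censoring date in a PFS analysis should be the last date on which the subject was known to be progression-free. A scan that could not be read does not establish that. The rule nevertheless carries the subject forward to it as event-free, and progression cannot be recorded for that subject in the interval.

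The situation can plausibly arise. The IRC reads are primary for PFS and DOR (Section 6). If the investigator calls progression and the IRC reads that scan as NE, Section 6 asks for no further end-of-treatment scan, because that scan is for withdrawals other than progression on imaging. Without a later IRC progression or a qualifying death, the subject is event-free up to the very scan on which the investigator saw progression.

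The trial has one arm (Section 3.2), so no comparator carries the same distortion. PFS and DOR would be read as absolute figures, and they would err in one direction.

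**Working it through.** The SAP states no sample-size, event or precision figure for PFS or DOR, so there is no figure of the plan's own to reproduce.

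**Direction.** Kaplan-Meier multiplies factors 1 − d/n over event times, with d events and n at risk. Let m subjects have their last readable scan before an event time and their final NE scan at or after it.

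- Censoring at the last evaluable scan: factor = 1 − d/n
- Censoring at the NE scan: factor = 1 − d/(n + m)
- Difference = d·m / [n(n + m)] ≥ 0

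No factor falls, so the curve is equal or higher. Two conditions apply. Event status must be the same under both rules, and only NE scans at the end of follow-up matter; an NE scan followed by an evaluable one leaves the date unchanged. DOR uses the same rule and estimator, so the same algebra applies. DOR was not simulated separately.

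**Size.** From the SAP come the scan schedule (Weeks 8, 16, 24, then every 12 weeks) and the rule itself. The NE rate and the true PFS are not given. Two sets of assumptions were simulated, comparing the two censoring dates.

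*Set A*: exponential progression with median 26 or 43 weeks; 20% or 35% stopping drug without progression by Week 48; NE in 5–10% of all scans or 30–60% of end-of-treatment scans; administrative cut at 24 to 90 weeks; 40,000 subjects.

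- 2% to 18% of subjects were affected, each gaining about 7 to 11 weeks of event-free time on average.
- 24-week PFS rose by 0.2 to 0.9 points and 48-week PFS by 0.2 to 1.1 points.
- With median 43 weeks and 35% stopping: 10% NE at every scan gave 0.467 − 0.458 = 0.9 points; 60% NE at end of treatment gave 0.464 − 0.454 = 1.0 point.
- In 600 single trials of 125 or of 60 subjects (same median and stopping rate), the gain was usually 0.3 to 1 point, reached 2 to 6 points at the extremes, and was never negative.

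*Set B*: exponential progression with median 6, 9 or 12 months; uniform follow-up of 6 to 21 months; 2% dropout per month; NE either independent of progression or 3 times as likely once progressed; 60,000 subjects per scenario, 18 scenarios. Here every NE read ends follow-up, so this is the heavier set by construction.

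| Chance per scan of a final NE read | Subjects ending on NE | Rise in 48-week PFS under the SAP rule |
|---|---|---|
| 2% | 6–9% | 0.7 to 1.2 points |
| 5% | 14–21% | 1.8 to 3.2 points |
| 10% | 26–38% | 3.7 to 6.5 points |

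The rise was positive in all 18 scenarios. The Kaplan-Meier median was one visit later under the SAP rule in 3 of 18 and unchanged in the other 15.

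**Does last-evaluable censoring recover the right answer?** Median 9 months, 5% chance per scan:

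| | SAP rule | Last evaluable | No NE scans |
|---|---|---|---|
| NE independent of progression | 44.7% | 42.7% | 42.7% |
| NE 3 times as likely after progression | 48.9% | 46.2% | 42.8% |

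With independent NE, censoring at the last evaluable scan came within 0.2 points of the no-NE result in every scenario. With informative NE it removed only part of the bias.

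**The case against.** The rule is explicit, prespecified and reproducible. PFS and DOR are secondary, with no stated hypothesis or threshold. At a 48-week PFS of 0.46 and n = 125, the binomial standard error is √(0.46 × 0.54 / 125) = 4.5 points, so a bias of 1.1 points is about a quarter of one standard error. This stands as an argument about size. It does not remove a one-sided error that costs little to avoid.

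Section 6.1 describes NE as a best overall response for a subject, not as a read at one visit. Visit-level reading belongs to the Imaging Charter and the protocol, which are not at hand. This also stands: the fixed direction is conditional on NE reads carrying no progression information.

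Four stronger readings are tempting, and the SAP does not support them:

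- *That the planned sensitivity analyses cannot reveal the effect.* The three visible ones keep the rule, but a redacted block follows. The appendix also lists Tables 2.4.5 and 2.5.5 as investigator-assessed sensitivity analyses, separate from the ordinary investigator tables. A further analysis cannot be excluded.
- *That the SAP is stricter on NE for lymph node response.* Section 3.1.1 limits that analysis to subjects with an evaluable post-baseline assessment. This takes unevaluable subjects out of the denominator and is not a stricter rule.
- *That PFS is overstated by several points.* This needs NE rates that nothing in the SAP supports.
- *That a subject with progression after two missed scans is censored at the progression scan itself.* The text does not limit which scan counts as last, but this is a separate wording gap and does not bear on NE. The natural intention is the last scan before the gap.

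**Conclusion.** The point holds as a stated rule that gives PFS and DOR estimates equal to or higher than censoring at the last evaluable scan, provided NE reads carry no progression information. The size cannot be fixed from the SAP. Under the assumed rates it is about 0.2 to 1 point on 48-week PFS when final NE scans are uncommon. In the heavier set it is about 2 to 3 points when 14–21% of subjects end on an NE scan, and 3.7 to 6.5 points only when 26–38% do. It is probably small against sampling error, and the Kaplan-Meier median usually does not move. The ORR test does not use this rule and is unaffected. The change is worth making because the direction is predictable, there is no control arm, and the cost is low.

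**What to change.** Replace the censoring sentence in Section 6.4.2.1 with wording to this effect:

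> *A subject to be censored for PFS or DOR is censored at the latest evaluable tumor assessment showing no progression (NE reads do not count) that precedes the reason for censoring: the start of new anti-tumor therapy, or the first of a run of two or more missed assessments. For PFS, a subject with no evaluable post-baseline assessment and no event is censored on Study Day 1.*

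DOR needs no Day 1 rule, because a responder always has an evaluable assessment.

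Two further statements are needed:

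- Whether an NE scan counts as missing under the two-consecutive-missing rule. If it does, a sequence of SD, NE, NE, PD changes from an event to a censored observation, which can raise PFS and work against the correction.
- Which reads count as evaluable, including ND and a progression set aside under Section 6.1.

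Keep censoring at the NE date as a sensitivity analysis, and report how many subjects end on an NE scan so that the size can be judged.

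The cost is one sentence, one change to the derivation, slightly shorter follow-up and slightly lower PFS and DOR estimates. If unreadable scans are more likely after progression, some upward bias will remain.
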